7.7.1.6. Immunogenicity Against the Vector

For immunogenicity against the Ad26 vector backbone (Adenovirus neutralization by neutralization assay) following statistics will be calculated: geometric mean and corresponding 95% CI of the actual values, and number and percentage of participants with a positive sample.

If only one time point is available, then actual values at that single time point will be shown as a dot plot. If multiple time points are available, then GMT plots over time, combining the regimens in one graph (without individual participant dots) will also be generated. In addition, subject profiles will then also be created.

7.7.1.7. Statistical Modeling of the Immune Responses

Statistical modeling will be undertaken to assess the influence of demographic variables and baseline characteristics on selected immune responses. These analyses will be performed on the PPI analysis set, excluding participants in the regimens that received no active vaccine. The following are pre-planned statistical analyses:

- Linear regression analysis of 28 days post Dose 1, pre-Dose 2 and of 28 days post Dose 2 psVNA titers on demographic and baseline characteristics and control variables, using pooled data from all regimens and all cohorts.
- One model for 28 days post Dose 1, one for pre-Dose 2 and one for 28 days post Dose 2
- psVNA titers enter the model on the \log_{10} scale.

- Demographic variables: age (continuous), BMI (continuous), sex (categorical: male vs. female), race (categorical: Black or African American vs. White vs. Other).
- Baseline characteristics: baseline SARS-CoV-2 seropositivity status (categorical: Positive vs. Negative) and baseline VNA titers against the Ad26 vector (continuous, on the \log_{10} scale).
- Control variables: single-dose vs. two-dose regimen and high-dose vs. low dose regimen.
- Linear regression analysis of 28 days post Dose 1, pre-Dose 2 and of 28 days post Dose 2 wild type VNA titers on demographic and baseline characteristics and control variables, using pooled data from all regimens and all cohorts. Same considerations as for psVNA titers.
- Linear regression analysis of 28 days post Dose 1, pre-Dose 2 and of 28 days post Dose 2 ELISA antibody concentrations on demographic and baseline characteristics and control variables, using pooled data from all regimens and all cohorts. Same considerations as for psVNA titers.
- Penalized logistic regression analysis (using Firth's method) of 28 days post Dose 1, pre-Dose 2 and of 28 days post Dose 2 responder status for psVNA on demographic and baseline characteristics and control variables, using pooled data from all regimens and all cohorts.
- One model for 28 days post Dose 1, one for pre-Dose 2 and one for 28 days post Dose 2
- psVNA responder status enters the model as a categorical variable (coded 1 for responder and 0 for non-responder).
- Other considerations as for the linear regression models

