7. STATISTICAL ANALYSES

7.1. General Considerations

7.1.1. Study Phases

A baseline (or reference) value will be defined as the value of the last available assessment prior to the first vaccination on Day 1.

The safety analysis will present all results by phase (cf. section 7.1.2 for phase definitions). Immunogenicity results will be presented per scheduled time point as appropriate. Efficacy analyses will present results by phase or pooled for the entire study, as appropriate. Listings will be shown per phase and time point.

Study day or relative day is defined as follows:

Study Day = visit date - date of Day 1 + 1; if visit date \geq date of Day 1 (date of first vaccination).

Study Day = visit date - date of Day 1; if visit date $<$ date of Day 1 (date of first vaccination).

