7.7.1.5. Immunogenicity Against the Insert

7.7.1.5.1. Humoral Assays

For **VNA** (both wild-type virus and pseudovirion expressing S protein, as available), the following statistics will be calculated: N, geometric mean and corresponding 95% CI of the actual values, fold increase from baseline, fold increase from pre-dose 2 (if applicable, i.e. only for cohorts where a second dose is given in the primary regimen and for time points after dose 2), fold increase from pre-booster dose 1, fold increase from pre-booster dose 2, fold increase from pre-booster dose 3 (if applicable, i.e. only for cohorts 2a and 2b where booster doses are given and for time points after the said booster dose).

For the calculation of the geometric mean and its corresponding 95% CI, the arithmetic mean and its corresponding 95% CI are calculated on the \log_{10} transformed values. These values are back transformed to provide the geometric mean and its corresponding 95% CI.

For wild type and pseudovirion VNA separately:

- A sample will be considered positive if the value is strictly greater than the LLOQ ($>\text{LLOQ}$).
- Responder definition. A post-baseline sample will be considered a responder if at least one of the following conditions is satisfied:
 - The baseline sample value is less than or equal to the LLOQ ($\leq\text{LLOQ}$) and the post-baseline sample is strictly greater than the LLOQ ($>\text{LLOQ}$)
 - The baseline sample value is strictly greater than the LLOQ ($>\text{LLOQ}$) and the post-baseline sample value represents an at least 4-fold (≥ 4 -fold) increase from the baseline sample value.

Actual values are tabulated and shown as dot plots with dots for participant values, and the corresponding geometric mean and 95% CI per time point for each assay. In addition, GMT plots over time, combining the regimens in one graph (without individual participant dots) will also be generated.

Participant profiles of the actual values over time will be graphically presented.

Reverse distribution curves of the actual values are provided for selected time points.

In the graphs, original values will be displayed on the \log_{10} scale.

Further details and/or updated rules may be provided in the DPS.

For **S-ELISA**, the same as above applies.

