7.7.4. Definition of Subgroups

Selected safety and immunogenicity analyses will be conducted by the seropositivity status (positive vs. negative) of the participant. A participant will be considered seropositive if:

1. The serological test for SARS-CoV-2-specific antibodies at baseline (if available) is positive

Note: in case multiple test results are available (IgG, IgM, IgA, no isotype specified), then as soon as one of the test results is positive, the participant will be considered seropositive.

OR

2. The S ELISA immunogenicity readout on Day 1 is considered positive.

At the time of first interim analysis of a cohort, S ELISA Day 1 data for that cohort may not be available at the time of the CRF database snapshot or lock. In that case, participant serostatus will be based solely on the serological test for SARS-CoV-2-specific antibodies at baseline. As of the second interim analysis, it is expected that S ELISA Day 1 data will have become available for the participants, so that both criteria can (and will) be applied.

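### The linear immune-response models reduce the SARS-CoV-2 baseline to serostatus yes/no, so they cannot show whether response depends on starting level; the precision lost is small

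*SAP*

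**What the plan says.** SAP section 7.7.1.7 states that the models are to "assess the influence of demographic variables and baseline characteristics on selected immune responses". They use the per-protocol immunogenicity set, leave out regimens without active vaccine, and pool all other regimens and all cohorts.

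Two baseline immune terms are listed. For the insert it is "baseline SARS-CoV-2 seropositivity status (categorical: Positive vs. Negative"). For the vector it is "baseline VNA titers against the Ad26 vector (continuous", on the log10 scale). The wild-type VNA and ELISA models inherit this list: "Same considerations as for psVNA titers".

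The baseline value of each modelled assay is planned. Section 7.1.1 defines baseline as "the value of the last available assessment prior to the first vaccination on Day 1". Section 7.7.1.5.1 lists for VNA the "geometric mean and corresponding 95% CI of the actual values, fold increase from baseline", and applies the same to S-ELISA.

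Section 7.7.4 classes a participant as seropositive if any baseline serology result is positive, or if "The S ELISA immunogenicity readout on Day 1 is considered positive". Section 7.7.1.5.1 gives the cut-off, stated for VNA and carried over to S-ELISA: "A sample will be considered positive if the value is strictly greater than the LLOQ".

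Section 6 excludes natural infection occurring after screening from the per-protocol immunogenicity set, so that rule leaves in participants who were already seropositive at baseline. Section 7.7.1.4 says that no formal immunogenicity hypothesis is tested.

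**The concern.** The stated aim is to learn how baseline characteristics influence response, and starting level against the insert is one of them. A two-level term gives a just-positive and a strongly positive participant the same fitted value. In the two VNA models the modelled assay plays no part in the classification. In the ELISA model it is one of two criteria, and is still dichotomised. A single serostatus coefficient therefore averages over a mixed group, and no coefficient describes the slope on starting level. Any variation explained by starting level within the seropositive group stays in the residual. The same covariate list keeps the vector baseline continuous, so the SAP already accepts a continuous baseline titre in these models.

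**Working it through.** The SAP states no sample size, SD, correlation or seropositive share for these models, so there is no planned figure to reproduce. All sizes below are conditional.

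**Assumed inputs.** N = 800, in line with the 860 active participants in section 7.7.3 (models of later time points may have fewer). Residual SD σ = 0.45 log10. SD of baseline log10 level among seropositive participants s = 0.5. Slope b = 0.3 to 0.6. Seropositive share q varied. Seronegative participants share one baseline value, and every seropositive participant has a measurable one.

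**Precision of the other coefficients.** Without the baseline value, the pooled residual variance is σ² + q·(b·s)². With it, the residual variance is σ². The standard error therefore falls by 1 − 1/√(1 + q·(b·s/σ)²).

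- b = 0.3: (0.15/0.45)² = 0.111
- b = 0.6: (0.30/0.45)² = 0.444
- At q = 10%: 1 − 1/√1.0111 = 0.55%, and 1 − 1/√1.0444 = 2.15%

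**Detectability of the slope.** SE(b) ≈ σ/(s·√(qN)), and power ≈ Φ(b/SE − 1.96).

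- At q = 5%, 40 participants carry the slope: SE = 0.45/(0.5·√40) = 0.142.
- b/SE is then 2.11 for b = 0.3 and 4.22 for b = 0.6, giving power of about 0.56 and 0.99.

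| q | SE reduction, formula (b = 0.3; 0.6) | SE reduction, simulated | Slope power, formula | Slope power, simulated |
|---|---|---|---|---|
| 2% | 0.11%; 0.44% | 0.04–0.4% | 0.26; 0.76 | 0.24–0.71 |
| 5% | 0.28%; 1.09% | 0.2–1.0% | 0.56; 0.99 | 0.54–0.98 |
| 10% | 0.55%; 2.15% | 0.4–1.8% | 0.85; 1.00 | 0.81–1.00 |

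The simulations compared ordinary least squares with and without the baseline value, 400 data sets per setting. The formula is slightly optimistic, in part because it ignores the extra degree of freedom.

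**Check in terms of correlation.** Let ρ be the baseline to post-dose correlation among seropositive participants, with equal outcome variance in both serostatus groups. The SE reduction is then 1 − √(1 − q·ρ²). For ρ = 0.3 to 0.7 it is 0.23–1.23% at q = 5% and 0.45–2.48% at q = 10%. It exceeds 5% only with q of 20 to 30% and ρ of about 0.7.

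**Values at or below LLOQ.** Serostatus and being above LLOQ on the modelled assay need not coincide. A participant positive on serology alone can be at or below LLOQ, and a seronegative one can be above it on VNA. A constant imputed below LLOQ is then not absorbed by serostatus. Section 7.7.1.2 uses LLOQ/2 for geometric means and LLOQ for fold increases. If 30% of seropositive participants are below LLOQ, simulation gives:

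- true slope 0.30: about 0.30 with LLOQ/2, but 0.37–0.38 with LLOQ
- true slope 0.60: 0.61 with LLOQ/2, but 0.75 with LLOQ

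An indicator for Day 1 at or below the assay's LLOQ removes this dependence on the constant. The slope then rests on fewer participants over a narrower range, so the powers above are upper figures.

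**The case against.** The strongest reply is that this is a preference and not an error. Serostatus is the SAP's own baseline classification, used throughout the safety and immunogenicity analyses, and using it here is consistent. No Ad26 serostatus subgroup is defined, so a continuous term is natural for the vector. Fold increases, baseline-dependent responder status, individual profiles and results by serostatus already show starting level descriptively. An added covariate also has costs. Section 7.7.1.1 warns that not every assay may be available for every analysis, section 7.7.4 that Day 1 S-ELISA may be missing at a cohort's first interim, and section 7.7.1.2 that missing immune data are not imputed.

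Most of this stands. There is no contradiction in the SAP, and the costs belong in the fix. What remains is that none of the planned displays estimates a slope on starting level, which falls within the models' stated aim.

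A reader might infer that the yes/no term costs material precision. The documents do not support that, because they give no seropositive share and the loss scales directly with it. A reader might also infer that the models ignore baseline immunity. They do not: serostatus and the Ad26 titre are both included.

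**Conclusion.** The point holds as a minor improvement. The linear models cannot show whether response depends on starting level among participants with a measurable baseline, although the required value is planned. The precision gain is about 1% or less of the standard error at up to 5% seropositive and about 0.4 to 2% at 10%, for slopes of 0.3 to 0.6. The slope is well estimated only if about 5 to 10% or more are seropositive, and towards the upper end of that range if the slope is shallow or some seropositive participants are below LLOQ. All of this rests on the assumed N, SDs and slopes and on a share that the SAP does not give. It would be too strong to call the planned models invalid or to say that a trial conclusion is at risk: they are exploratory and no formal hypothesis depends on them.

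**What to change.** In section 7.7.1.7, for each linear model:

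- Keep serostatus, and add the log10 Day 1 value of the modelled assay together with an indicator for Day 1 at or below that assay's LLOQ. The slope then does not depend on the imputed constant.
- In the S-ELISA model, if every seropositive participant is above LLOQ, the indicator duplicates serostatus and one of the two is dropped.
- Report this model beside the planned one, because the serostatus coefficient changes meaning once starting level is included.
- At early interims where Day 1 values are not yet available, run the planned model only.

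Leave the Firth responder model as it is. Its outcome is already defined from the baseline value, so a baseline term there raises separate problems.

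The cost is one or two degrees of freedom per model and the loss of participants without a Day 1 value for that assay. No new data collection is needed.

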7.7.1.8. Immunogenicity analyses after receipt of the ad hoc booster vaccination

Study participants who receive the ad hoc booster vaccination, will be removed from the main immunogenicity analyses as of that point in time^{a,b}. A separate immunogenicity analysis will be conducted on the study participants who received the ad hoc booster vaccination, starting at the time of the ad hoc booster vaccination and showing their immune responses at each subsequent time point, as available. The statistical analysis will be descriptive. It will show study participants according to their original vaccination regimen in tables, listings and figures. In addition, the analyses may also be conducted separately by subgroups of study participants who received a COVID-19 vaccine outside of the study vs study participants who did not receive a COVID-19 vaccine outside of the study. A distinction between mRNA vaccines vs other vaccines may be made, if the numbers are sufficiently high. Otherwise, this information will be included in the listings only.

^a Note that participants may already have been removed from the main immunogenicity analyses due to receipt of an unscheduled vaccine (either a COVID-19 vaccine received outside of the study or after crossing over from placebo to active within the study). Refer to the clinical trial protocol amendment 15, section 9.7 for more information.

^b Note that, unless the sample needs to be excluded from the analysis for reasons noted in the above footnote (or other reasons as noted elsewhere in the SAP, e.g. occurrence of a natural infection, etc.), the blood sample taken at the day of the ad hoc booster vaccination can be included in the main analysis. As such, it could both contribute to the main immunogenicity analyses (e.g. assess the long term immunogenicity profile) as well as to the analyses on the ad hoc booster (as a baseline).

Additional exploratory analyses may be conducted, such as but not limited to, statistical modeling to determine the effect of the time gap between the last vaccination and the ad hoc booster vaccination, and/or durability of the immune responses observed after the ad hoc booster. Additionally, analyses may be performed to assess the non-inferiority of post booster or post ad hoc booster responses vs. selected pre-booster or pre-ad hoc booster time points. These analyses may include assessments of the geometric mean ratio (GMR), the percentage responders, or other indicators for immune responses. As the protocol did not plan any formal non-inferiority analyses, there is no alpha spending and all analyses will be conducted at a nominal alpha level of 0.05 (two-sided). While the results of these analyses may be interpreted using the typical non-inferiority guidelines (e.g. the lower limit of the confidence interval around the GMR $>2/3$ and/or the lower limit of the confidence interval around the difference in responder percentage $>10\%$ would lead to concluding “non-inferiority”), it will be understood that these analyses are exploratory.

Moreover, alternative responder definitions may also be assessed in addition to or instead of the usual responder definition as described elsewhere in this SAP. For instance, the following responder definition may be used for the assessment of humoral responses:

A participant will be considered a “responder”, if:

- The baseline sample value is less than or equal to the LLOQ (\leq LLOQ, or another threshold/cut-off value as appropriate for the assay) and the post-baseline sample value is strictly greater than 4 times the LLOQ ($>4\times$ LLOQ, or another threshold/cut-off value as appropriate for the assay)
- The baseline sample value is strictly greater than the LLOQ ($>$ LLOQ, or another threshold/cut-off value as appropriate for the assay) and the post-baseline sample value represents an at least 4-fold (\geq 4-fold) increase from the baseline sample value.

It should be noted that the “baseline” refers to time points selected based on the purpose of the analysis. Commonly, “Day 1” or “Pre-boost” is chosen as the baseline, but for non-inferiority (or other exploratory) analyses, the baseline can be another time point which is more relevant and of more substantive interest, e.g. 28 days post dose 1 or 28 days post dose 2. Similarly, the “post-baseline” timepoint refers to timepoint relevant to the analysis purpose. Commonly, all post-baseline time points will be assessed, but for some analyses, such as (but not limited to) non-inferiority analyses the focus may be on a specific time point or a few time points of interest (e.g. 14 days post booster, 28 days post ad hoc booster, etc.).

Details of the analyses will be provided in the DPS.

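### The example non-inferiority rule for responder percentage (lower limit above +10%) is printed as a superiority rule and contradicts the GMR rule beside it

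*SAP*

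**What the plan says.** In SAP Section 7.7.1.8, after the descriptive ad hoc booster analyses, the plan adds an optional aim: "assess the non-inferiority of post booster or post ad hoc booster responses vs. selected pre-booster or pre-ad hoc booster time points". The results "may be interpreted using the typical non-inferiority guidelines", and two examples follow, joined by and/or and leading to the same conclusion of non-inferiority:

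- for the geometric mean ratio, "the lower limit of the confidence interval around the GMR $>2/3";
- for responders, "the lower limit of the confidence interval around the difference in responder percentage $>10" per cent.

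On error control the section says "all analyses will be conducted at a nominal alpha level of 0.05 (two-sided"), and "As the protocol did not plan any formal non-inferiority analyses, there is no alpha spending". It closes with "Details of the analyses will be provided in the DPS". It does not state the direction of subtraction, the interval method, the sample size or the expected responder rates. No other section of the SAP gives a non-inferiority margin for responder percentage.

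**The concern.** A non-inferiority rule tolerates a stated loss, so its threshold lies on the unfavourable side of no difference. The GMR threshold does: 2/3 is below 1. The responder threshold does not: +10 points is above 0. On the same data the two examples can therefore give opposite answers, although both are offered as ordinary non-inferiority guidelines.

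At stake is the label put on an exploratory comparison. Applied literally, the rule would withhold the non-inferiority label from a booster response that matches a high reference response. If the rule is silently read with a minus sign, the report departs from the approved plan. The estimates and intervals are the same either way.

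**Working it through.** **Inputs from the SAP.** Responder threshold +10 points, GMR threshold 2/3, two-sided 0.05, so z = 1.96 (all Section 7.7.1.8). The Newcombe formula is printed in Section 7.7.2 for another analysis and is borrowed here, with Wald as a variant.

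**Assumed, because the SAP gives none.** 25 to 200 participants per time point, true responder rates of 50% to 95%, and the two time points treated as independent. The plan states no power or sample size for this analysis, so there is no figure of its own to reproduce.

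**Step 1: equal observed percentages.** The difference is 0. The lower limit of an interval that contains its own point estimate cannot exceed that estimate, so it cannot exceed 0 and the rule fails. Example: 90% and 90%, 100 each. The Wilson limits are 0.8256 and 0.9448. The Newcombe lower limit is 0 − √[(0.9 − 0.8256)² + (0.9448 − 0.9)²] = −√(0.00553 + 0.00201) = −0.087. That is above −10 points and below +10 points.

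**Step 2: high reference rate.** If the observed reference is 90% or more, the observed difference is at most 100 − 90 = 10 points, so the lower limit cannot lie above 10. With 100% against 90%, 100 each, it is +4.2 points.

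**Step 3: what does pass.** With 100 each, 91% against 70% gives 0.21 − √[(0.91 − 0.8377)² + (0.7811 − 0.70)²] = 0.21 − 0.1086 = +0.101, just enough. Against 80%, the post-booster figure must reach 99%. The rule can be met, but only as superiority by more than 10 points.

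**Step 4: chance of passing**, by exact enumeration of two independent binomials:

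| True post / reference | n each | Above −10: Newcombe | Above −10: Wald | Above +10 (printed) |
|---|---|---|---|---|
| 50% / 50% | 25 | 10% | 10% | 0.33% Newcombe, 0.77% Wald |
| 90% / 90% | 100 | 62% | 67% | at most 0.001% |
| 95% / 95% | 50 | 51% | 66% | below 0.001% |
| 95% / 95% | 100 | 83% | 89% | about 3 in 100 million |
| 95% / 95% | 200 | 99% | 99% | below 0.001% |
| 95% / 85% | 100 | 99.8% | 99.8% | 2% |

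Across the equal-rate cases the printed rule passes at most 0.77% of the time. In the last row it passes only 2% of the time although the post-booster rate is truly 10 points higher.

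**Step 5: the companion rule.** At an observed GMR of 1 with 100 per time point, the lower limit is 10^(−1.96 × SD × √(2/100)). For an assumed log10 SD of 0.4, 0.5 or 0.6 this is 0.77, 0.73 or 0.68, all above 2/3. With 50 per time point the limits are 0.70, 0.64 and 0.58, so only the first passes. Equality can therefore satisfy the GMR rule given enough precision, whereas no sample size lets observed equality satisfy the responder rule.

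**Step 6: reversed subtraction.** If the difference were reference minus post-booster, non-inferiority would need an upper limit below +10 points. A lower limit above +10 would then show the booster response to be worse. Neither direction rescues the text.

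**The case against.** The strongest reply is that the line binds nothing. The analyses are optional, the thresholds are an example, no alpha is spent, Section 7.7.1.4 says that no formal immunogenicity hypothesis is tested, and details are left to the DPS, which is not at hand. The text invokes usual practice and sets the line beside a GMR limit of 2/3, so many readers would supply the minus sign themselves. All of this stands, and it lowers the severity. It does not make the printed threshold right.

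The text was also read from PDF, and a minus sign could have been lost in that step. Minus signs do survive in the formulas of Section 7.7.2 and nothing in this sentence shows a loss, but it cannot be excluded.

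The illustration rests on assumed rates and sample sizes and on independence, whereas the comparison would largely be within participant. A paired interval would change the percentages in Step 4, but not Steps 1 and 2.

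A reader might infer three stronger things that the SAP does not support. One is that equal responses can never pass: this is strict only for equal observed percentages, and for equal true rates the chance is small but not zero. Another is that any improvement fails: a large gain over a lower reference passes, as Step 3 shows. The third is that the sponsor is committed to a wrong decision: the rule is an optional way to interpret exploratory results.

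**Conclusion.** The point holds for the text as printed. The responder example requires superiority by more than 10 points and contradicts the GMR example in its own sentence. Two results need no assumption about sample size or pairing: observed equality always fails, and an observed reference of 90% or more makes the rule impossible to meet. The pass rates (below 1% at equal true rates; 83% to 89% against essentially 0 at 95% and 95% with 100 each) depend on the assumed sample sizes, rates and independence. No primary or secondary endpoint depends on the rule, so the severity is minor to moderate.

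**What to change.** First check the source file for a minus sign lost in conversion. If it is absent there too, reword the responder example as: lower bound of the two-sided 95% CI for the responder-percentage difference, post-booster minus reference time point, above −10 percentage points. The sponsor should confirm the size of the margin, since −10% is not stated in the SAP. Then make the DPS agree, including the direction of subtraction. The cost is a minus sign and a short definition in one sentence, plus a check of the DPS. No data collection or endpoint changes.
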